## 6.7. Protocol Therapy Discontinuation

In addition to discontinuation from therapy related to toxicities as outlined above, a subject will also be discontinued from protocol therapy and followed per protocol under the following circumstances outlined below. The reason for discontinuation of protocol therapy will be documented on the electronic case report form (eCRF).

The Prostate Cancer Working Group 3 (PCWG3) recognizes that favorable effect of experimental therapies on PSA may be delayed for  $\geq 12$  weeks and recommends continuing treatment through early rises for a minimum of 12 weeks unless there is other evidence of progression.

PCWG3 recommends continuing experimental therapies for subjects who experience PSA rise after initial decline, in the absence of any radiographic or clinical progression. However, subjects in this trial do have access to a standard-of-care treatment in the form of ADT which can be used to delay development of metastatic disease, although a convincing survival benefit has not been established in this setting. This trial requires treatment discontinuation only for the reasons below, but investigators are advised to use discretion for patients with rapidly increasing PSAs (after 12 weeks of treatment). Patients believed to be clinically benefitting, for example based on decreased PSADT after starting nivolumab, could be continued on treatment at the investigator's discretion.

- Documented metastases on imaging (see Section 9 for definitions).
- Completed 2 years of treatment with nivolumab
- Site investigator determines a change of therapy (i.e. starting ADT) would be in the best interest of the subject
- Subject or legal representative (such as a parent or legal guardian) withdraws consent and requests to discontinue protocol therapy, whether due to unacceptable toxicity or for other reasons
  - In a subject decides to prematurely discontinue protocol therapy (“refuses treatment”), the subject should be asked if he or she may still be contacted for further

scheduled study assessments. The outcome of that discussion should be documented in both the medical records and in the eCRF.

- Unacceptable adverse experiences
- Intercurrent illness that prevents further administration of treatment
- Protocol therapy is interrupted for > 6 weeks (calculated from the date of the first missed dose). Any potential exceptions to this criteria must be discussed with and approved by the PI.
- Noncompliance with protocol treatment or procedure requirements
- The subject is lost to follow-up
- Administrative reasons

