	
nivolumab. PD-L1 tumor-cell expression on primary tissue samples (prostatectomy or diagnostic core biopsies) will be prospectively assessed and used to assign subjects to one of two groups (positive vs. negative). Next-generation sequencing will also be performed upon enrollment but will be used only for exploratory studies. If subjects experience PSA stabilization (<10% increase from baseline) or responses, they will continue nivolumab for up to 2 years in the absence of progression to metastatic disease or unacceptable toxicity. Patients who have stabilization of PSA in the absence of radiographic or clinical progression may also continue treatment. Patients who have isolated PSA progression at 12 weeks can be continued on treatment by investigator's discretion if they are believed to be clinically benefitting (for example, if they experience decreased PSA doubling time) and have not demonstrated symptomatic or radiographic evidence of metastatic disease.

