## **2.2. Endpoints**

### **2.2.1. Primary Endpoint**

The primary endpoint is disease control, defined as PSA at 12 weeks less than 10% above baseline, or below baseline, and no symptomatic/radiographic progression, after 12 weeks of nivolumab treatment.

The expected increase in PSA at 12 weeks depends on doubling time. Based on the doubling time formula,  $\text{doubling time} = \log(2)/\log(1 + \text{growth rate})$ , a patient with a 10-month doubling time (the longest allowed under the exclusion criteria) would be expected to have an approximately 7.18% growth rate per month. PSA increase over 3 months (12 weeks) without intervention would be expected to be 23%. Faster doubling time would result in faster growth rate. Therefore, disease stability will be considered a PSA rise of less than 10% above baseline at 12 weeks. (This is in contrast with PCWG3, which considers PSA progression to be rise of at least 25% of baseline; as noted above, this criterion is too lenient in this setting given the expected PSA rise in the absence of intervention).

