### 9.1. Definitions

- Disease control rate: please see Study Endpoints (section 2) above
- Maximal PSA change: Best PSA response divided by baseline PSA x 100%]
- Best PSA response: Baseline PSA minus lowest on-study PSA at any time
- PSA doubling time (PSADT): calculated as per the PCWG3 and Memorial Sloan Kettering Cancer Center calculator ([https://www.mskcc.org/nomograms/prostate/psa\\_doubling\\_time](https://www.mskcc.org/nomograms/prostate/psa_doubling_time)) with linear regression model of natural logarithm of PSA and time, based on:
  - At least 3 consecutive PSA values with each value  $\geq 0.2$  ng/mL
  - Interval between first and last PSA values is  $\geq 8$  weeks but  $\leq 12$  months

PSADT should be calculated based on pre-study PSAs and based on the last 3 PSAs prior to EOT. If subject comes off trial prior to cycle 4, then EOT PSADT cannot be calculated since the first of three values would coincide with baseline value at cycle 1 day 1.

- Radiographic progression to metastatic disease:
  - Lymph nodes must have grown by at least 5 mm in the short axis from baseline or nadir and be  $\geq 1.0$  cm in short axis to be considered to have progressed. If the node progresses to  $\geq 1.5$  cm in the short axis, it is considered pathologic (metastatic) in the absence of alternative explanation. Nodes that have progressed to between 1.0 and less than 1.5 cm are subject to clinical discretion.
  - New unequivocal visceral lesions are determined by RECIST 1.1 criteria
  - Bone metastases are difficult to assess. PCWG3 recommends recording the date of unequivocal development of new sites on bone scintigraphy, then continuing therapy (assuming it is well tolerated and there is no clinical reason to discontinue it) until two additional new lesions are detected. If two new lesions are subsequently detected, these must be confirmed at the time of next bone scan; if confirmed, date of progression is the date these two new lesions were initially detected. **All cases of progression called on bone scan must be reviewed by the overall PI to confirm adherence to PCWG3 guidelines.** Sites should ask interpreting radiologists to enumerate bone lesions for all such cases.

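### The Synopsis and Section 6.7 give a decreased PSADT as the example of clinical benefit, but a shorter positive doubling time means PSA is rising faster

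*Combined protocol and SAP*

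**What the plan says.** Two places in the combined protocol and SAP tell investigators when nivolumab may continue despite a rising PSA.

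- **Synopsis, Study Design.** Men with isolated PSA progression at 12 weeks and no symptomatic or radiographic metastatic disease may continue at the investigator's discretion "if they are believed to be clinically benefitting (for example, if they experience decreased PSA doubling time").
- **Section 6.7.** After advising discretion where PSA is climbing quickly beyond 12 weeks, the text adds: "Patients believed to be clinically benefitting, for example based on decreased PSADT after starting nivolumab, could be continued on treatment at the investigator's discretion".

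In each place this is the only example of benefit given.

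Section 2.2.1 fixes the meaning of the term. It sets doubling time = log(2)/log(1 + growth rate), works the case of "a patient with a 10-month doubling time (the longest allowed under the exclusion criteria"), and concludes: "Faster doubling time would result in faster growth rate". Section 1.1 and the eligibility criterion of PSADT below 10 months likewise treat a short PSADT as high risk. No section redefines the term.

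On calculation, Section 9.1 says: "PSADT should be calculated based on pre-study PSAs and based on the last 3 PSAs prior to EOT", by regression of log PSA on time. Section 12.2.2 summarizes the change in PSADT through the change in PSA slope.

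**The concern.** The example of benefit and the formula point in opposite directions. A man whose doubling time has shortened, and is still positive, is getting worse faster than before he started drug. A man whose rise has slowed has a longer doubling time. He is the man a provision for continuing through PSA progression would be expected to help, and the example does not describe him.

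This is operative guidance and not background. The Synopsis makes believed benefit the condition for continuing after PSA progression at 12 weeks. Section 5.3.2 bars anti-androgens and GnRH agents on study, so continuing nivolumab means deferring ADT. A site that follows the example literally would have support for keeping men with accelerating PSA on nivolumab, and none for the men whose PSA has slowed.

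**Working it through.** **Inputs.** The formula and the 10-month case come from Section 2.2.1, the PSADT limit of under 10 months from Section 3.1, the 10% disease-control threshold from Section 2.2.1, and the regression definition from Section 9.1. As in Section 2.2.1, 12 weeks is taken as 3 months, and one cycle as 1 month. The individual PSADT pairs and PSA values below are illustrative assumptions.

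**Step 1: reproduce the plan's own figures.** Solving the formula for growth gives g = 2^(1/PSADT) − 1. At 10 months, g = 2^(0.1) − 1 = 7.18% per month, and the 3-month rise is 2^(3/10) − 1 = 23.1%. The plan states 7.18% and 23%, so both reproduce.

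**Step 2: direction.** The 3-month rise is 2^(3/PSADT) − 1 and the log-PSA slope is ln(2)/PSADT per month. Both fall steadily as a positive PSADT lengthens. Entry requires PSADT below 10 months. A man whose on-study PSADT is positive and shorter than his pre-study value is therefore rising faster than his own earlier rate, and by more than 23% per 3 months.

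**Step 3: the 10% threshold.** A 10% rise in 3 months corresponds to PSADT = 3 × ln(2)/ln(1.10) = 21.8 months. Under constant growth, disease control therefore needs a PSADT longer than that, or a flat or falling PSA.

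**Step 4: three illustrative men,** each with a pre-study PSADT of 9 months (3-month rise 2^(3/9) − 1 = 26.0%; slope 0.6931/9 = 0.0770 per month):

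| Man | On study | 3-month rise or week-12 change | Log-PSA slope per month | PSADT numerically decreased? | Actual course |
|---|---|---|---|---|---|
| A | PSADT 6 months | 2^(3/6) − 1 = 41.4% | 0.1155 (1.5 times) | Yes | Worse |
| B | PSADT 18 months | 2^(3/18) − 1 = 12.2% | 0.0385 (halved) | No | Slowed, but still PSA progression at 10% |
| C | PSA 10, 14, 13, 12 at cycles 1–4 | 12/10 − 1 = 20% above baseline | −0.0771 | Yes (−9.0 months) | Falling over the last three values |

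For C, the least-squares slope of ln(14), ln(13), ln(12) at months 1, 2, 3 is (2.4849 − 2.6391)/2 = −0.0771, and 0.6931/(−0.0771) = −9.0 months (−8.3 calendar months with 28-day cycles). This applies the three-value rule of Section 9.1, written for end of treatment, at week 12, where cycles 2 to 4 span 8 weeks. Section 9.1 supports that as the earliest point: "If subject comes off trial prior to cycle 4, then EOT PSADT cannot be calculated". C shows that PSA progression against baseline does not guarantee a positive on-study PSADT. The documents do not say how a negative slope is reported as PSADT.

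**Step 5: compare the two criteria.** Read literally, the decreased-PSADT wording groups A with C and leaves out B. A decreased slope relative to pre-study picks out B and C and excludes A, which is the right ordering in all three cases.

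**The case against.** The strongest reply accepts the slip and contests its weight.

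- **It is only an example.** The operative test is the investigator's belief and discretion, so the example formally excludes nobody. Section 6.7 also says "This trial requires treatment discontinuation only for the reasons below", and PSA progression is not among them. A man whose PSA has slowed may continue whatever the example says. This stands.
- **There are safeguards.** A listed reason for stopping is "Site investigator determines a change of therapy (i.e. starting ADT) would be in the best interest of the subject". The Synopsis requires no symptomatic or radiographic metastatic disease, imaging is due before cycle 4 and every third cycle thereafter, and documented metastases end treatment. These limit harm but do not correct the direction of the guidance.
- **A clinician would see the intended meaning.** That is likely, since the rest of the protocol treats short doubling times as unfavourable. Still, a protocol should not rely on sites reversing its words.
- **Harm from deferring ADT is not shown.** Section 6.7 says a survival benefit of ADT has not been convincingly established here, and Section 1.1 calls its timing controversial. This stands: the risk is a wrongly supported decision, not a demonstrated loss.
- **A falling PSA gives a negative PSADT, so a numerical decrease can go with benefit.** True, as in case C. But the same words also cover the accelerating man, so the phrase cannot separate benefit from harm.

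**Conclusion.** The concern holds. For any positive doubling time, the example of benefit in the Synopsis and Section 6.7 is reversed against the formula in Section 2.2.1. Allowing for negative slopes does not rescue the wording. The direction follows from the formula alone. The sizes (26.0% to 41.4% for a man matching the example, 26.0% to 12.2% for one who does not) rest on illustrative PSADT pairs and constant growth.

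The weight is minor to moderate. The text guides discretion and mandates nothing, and the disease-control endpoint, alpha, power and sample size do not depend on it. How many men it could affect cannot be estimated from the documents. It should be fixed because it is the only worked example sites have for this decision.

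**What to change.** In the Synopsis (Study Design) and in Section 6.7, replace the decreased PSA doubling time and decreased PSADT wording with: *decreased log-PSA slope relative to pre-study (i.e. lengthened PSADT, or falling PSA)*. This also covers negative slopes and matches how Section 12.2.2 already summarizes the change in PSADT. Send sites a short clarification.

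The cost is one phrase in two places plus that note. Design, sample size and analysis do not change.

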#### **6.8. Protocol Discontinuation**

If a subject decides to discontinue from the protocol (and not just from protocol therapy) all efforts should be made to complete and report study assessments as thoroughly as possible. A complete final evaluation at the time of the subject's protocol withdrawal should be made with an explanation of why the subject is withdrawing from the protocol. If the reason for removal of a subject from the study is an adverse event, it will be recorded on the eCRF.

## 7. STUDY CALENDAR & EVALUATIONS

Event	Screening	On Treatment (28-day cycles)	End of Study i	Follow-Up
	≤ 28 days prior to enrollment	Day 1 j	Within 30 days of last dose	Every 3 months until mPCa
Informed consent	X			
Confirmation of all eligibility criteria	X k			
Medical history a	X		X	X l
Prior systemic and radiation therapy b	X			
Physical examination c	X	X	X	
ECOG performance status	X	X	X	
Concomitant medication review	X	X	X	
Adverse Event review	X	X	X	X l (100 days after last nivolumab dose)
Chemistries d	X	X		
Hematology d	X	X		
TSH (with reflex free T4 testing if abnormal)	X	X		
Prostate-specific antigen e	X	X	X	
Archival tissue testing for PD-L1 expression and NGS f	X (After tissue pre-screen consent, prior to full informed consent, for patients enrolled under AM2)			
Blood for exploratory studies g		Cycles 1 and 2; q4 cycles beyond cycle 4 (C5, C9, etc.). Optional collection 1 week after cycle 1.	X	
Radionuclide bone scan and CT of abdomen/pelvis with contrast h	X	X (Prior to cycle 4 and every 3 rd cycle thereafter)		
Nivolumab administration		X		

Abbreviations: AE=adverse event; CBC=complete blood count; ECOG=Eastern Cooperative Oncology Group (performance score); EOS=end-of-study; mPca=diagnosis of metastatic prostate cancer; NGS=next-generation sequencing (e.g. Foundation One, OncoPanel).

- a Medical history: including relevant medical history collection, as well as Gleason score and TNM stage at diagnosis, results of any recent advanced imaging (Axumin, SPECT, choline, sodium fluoride, etc.)
- b Collect radiation site, administered dose per fraction and treatment duration, as well as any concurrent ADT and duration of ADT.
- c Physical examination includes height (at screening only), weight, vital signs, and general physical examination
- d Blood chemistry panel includes sodium, potassium, chloride, bicarbonate, calcium, blood urea nitrogen, creatinine, alkaline phosphatase, total bilirubin, AST, ALT. Testosterone will be drawn during screening to confirm castration but does not need to be repeated after screening. CBC must include white blood cell differential. CBC and chemistry testing may occur up to 48 hours prior to day 1 of each cycle. Labs obtained on cycle 1, day 1 do not need to re-meet eligibility criteria. Treatment may begin at each cycle before TSH result is available.
- e See requirements for baseline PSA testing in inclusion criteria.
- f Results of PD-L1 testing (including confirmatory testing if positive) must be obtained so that subject can be assigned to a study cohort BEFORE starting study treatment. Following PD-L1 testing and NGS, remaining tissue will be used for exploratory studies.
- g Exploratory studies include germline whole-exome sequencing performed at baseline, peripheral immunophenotyping, soluble biomarkers, ctDNA, and T-cell collections at specified intervals. Please see appendix 3 for details of blood collection. Research blood specimens will generally be collected with monitoring labs detailed in footnote d above. If standard labs are collected in advance, then research blood samples may be collected on the treatment day (before or after treatment). If research blood samples are inadvertently missed during collection of standard labs just before treatment, then the research blood samples may also be drawn post-treatment (same day).
- h Radiographic imaging will be obtained after every 3rd cycle until EOS. Radiographic imaging includes CT abdominal/pelvis with contrast (or MRI if contraindication to intravenous contrast) and bone scan. Radiographic imaging may occur up to 8 days prior to day 1 of the upcoming cycle, or on day 1 itself. Baseline imaging may include advanced imaging modalities as described in the eligibility criteria, assuming there is no radiographic evidence of disease.
- i End of study (EOS) assessments should be conducted in-person within 30 days after the last dose of nivolumab. AEs will also be assessed at 100 days after the last dose of nivolumab in the Follow-up Period (see footnote l). Patients must contact the study team regarding any significant toxicities or illnesses that occur within 100 days of last nivolumab dose, as SAEs must be reported during this time. For patients experiencing toxicities, EOS visits should occur every 2 weeks ( $\pm$  3 days) until toxicities resolve. Depending upon the toxicity, the every 2-week assessment may be accomplished via phone call, email or other avenues as appropriate. Mode of assessment will be at site investigator's discretion.
- j All visits have a window of  $\pm$  3 days.
- k Baseline imaging may be performed up to 60 days prior to enrollment.
- l Follow-up period will continue until documentation of metastatic disease (via radiographic imaging and/or biopsies). Follow-up may consist of medical record review (for patients treated at BIDMC) or contact via phone/email (for patients treated at non-BIDMC institutions). Data to be collected includes: date of initiation of any subsequent hormonal therapy, date of documented metastatic disease, and any other therapies received during follow-up period. If contact is made via phone/email with patient, then written documentation must be provided to confirm these dates and the diagnosis of metastatic disease. In addition, the research nurse must attempt to contact the patient (via phone or email depending on patient preference) approximately 100 days after the

last dose of nivolumab, +/- 1 week, to assess AEs. If the patient cannot be reached, attempts should be documented in the medical record and this will not be considered a deviation from protocol.

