SAFETY EVALUATION	
Toxicity will be graded using the NCI-CTCAE version 5.0.
 
Safety analyses will be conducted on all subjects who have received at least one dose of study drug, and will include the frequency of all AEs and laboratory abnormalities as well as the frequency of dose interruptions, dose reductions, and treatment discontinuations. All adverse events (AEs) must be attributed to study drugs unless there is a reasonably acceptable alternate cause for the AEs.
 
Additional safety assessments will include physical examination; medical history; ECOG performance status; weight; vital signs measurements; and clinical laboratory testing.

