## **5.2. Nivolumab Administration**

Nivolumab will be given on day 1 of a 28-day cycle at a dose of 480 mg intravenously (IV). All visits have a window of +/- 3 days (see Study Calendar, section 7).

The administration of nivolumab infusion must be completed within 24 hours of preparation. If not used immediately, the infusion solution may be stored under refrigeration conditions (2°C to 8°C, 36°F to 46°F) for up to 24 hours, and a maximum of 8 hours of the total 24 hours can be at room temperature (20°C to 25°C, 68°F to 77°F) and room light. The maximum of 8 hours under room temperature and room light conditions includes the product administration period. The unopened vials can be stored at room temperature (up to 25°C, 77°F) and room light for up to 48 hours.

Nivolumab injection is to be administered as an IV infusion over 30 minutes (acceptable window is 25 minutes to 40 minutes) through a 0.2-micron to 1.2-micron pore size, low-protein binding (polyethersulfone membrane) in-line filter at the protocol-specified doses

and infusion times. It is not to be administered as an IV push or bolus injection. Nivolumab can be infused undiluted or diluted so as not to exceed a total infusion volume of 160 mL. For patients weighing less than 40 kilograms (kg), the total volume of infusion must not exceed 4 mL per kg of patient weight.

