### **11.1. Definitions**

#### **11.1.1. Adverse Event (AE)**

An AE is any untoward medical occurrence whether or not considered related to the study drug that appears to change in intensity during the course of the study. The following are examples of AEs:

- Unintended or unfavorable sign or symptom
- A disease temporally associated with participation in the protocol
- An intercurrent illness or injury that impairs the well-being of the subject

Abnormal laboratory values or diagnostic test results constitute AEs only if they induce clinical signs or symptoms or require treatment or further diagnostic tests

Hospitalization for elective surgery or routine clinical procedures that are not the result of an AE (e.g., surgical insertion of central line) should not be recorded as an AE.

Disease progression should not be recorded as an AE, unless it is attributable to the study regimen by the site investigator.

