### 11.2.1. Adverse Events

- AEs will be recorded from time of signed informed consent until 100 days after discontinuation of study drug(s).
- AEs will be recorded regardless of whether or not they are considered related to the study drug(s).
- All AEs will be recorded in the subject's medical record and on the appropriate study specific eCRF form within OnCore.
- AEs considered related to study drug(s) will be followed until resolution to Grade  $\leq 1$  or baseline, deemed clinically insignificant, and/or until a new anti-cancer treatment starts, whichever occurs first.

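### The study calendar schedules no chemistry, haematology or TSH after the final nivolumab dose for men who finish 2 years or stop between a dose and the next Day 1

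*Combined protocol and SAP*

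**What the plan says.** In the Section 7 calendar, the Chemistries, Hematology and TSH rows ("TSH (with reflex free T4 testing if abnormal") have a mark at Screening and at on-treatment Day 1. Their End of Study (EOS) and Follow-Up cells are empty. In the same EOS column, physical examination, ECOG status, concomitant medication review, adverse event (AE) review, PSA and research blood are all marked.

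On timing, Section 5.2 states "Nivolumab will be given on day 1 of a 28-day cycle". Calendar footnote d allows chemistry and blood counts up to 48 hours before Day 1. Footnote i states "End of study (EOS) assessments should be conducted in-person within 30 days after the last dose of nivolumab".

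On what is to be reported, the synopsis says the safety analyses "will include the frequency of all AEs and laboratory abnormalities". Section 11.2.1 says "AEs will be recorded from time of signed informed consent until 100 days after discontinuation of study drug(s".

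After treatment stops, footnote i adds assessments every 2 weeks for men with toxicity, but "the every 2-week assessment may be accomplished via phone call, email or other avenues as appropriate". Footnote l adds an attempted phone or email contact at about day 100. Footnote g says of the exploratory samples: "Research blood specimens will generally be collected with monitoring labs detailed in footnote d above".

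**The concern.** A lab drawn on or just before the day of a dose says nothing about that dose. The next Day 1 normally supplies the check. A man with no next Day 1 has no scheduled check at all, and the 2-year completer, who follows the plan exactly, is always in that position.

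Two things are at stake. The first is patient safety. These men have rising PSA without metastases on conventional imaging and are largely symptom-free. Section 10.1.8 lists liver-test, thyroid and blood-count abnormalities and kidney injury among nivolumab's side effects. Section 1.9 notes that many of the grade 3-4 drug-related events in earlier trials were laboratory findings. Such changes can be silent.

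The second is completeness. The promised frequency of laboratory abnormalities would have no scheduled post-last-dose values for the men affected. If some sites draw safety labs with the EOS research blood and others do not, those values would also be uneven.

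**Working it through.** The plan states no figure on this point, so the check is of schedule and timing.

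**1. Is the gap real or a table-reading fault?**

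| Row | Screening | Day 1 | EOS |
|---|---|---|---|
| Chemistries | X | X | blank |
| Hematology | X | X | blank |
| TSH | X | X | blank |
| PSA | X | X | X |
| Research blood | blank | selected cycles | X |

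The PSA and research-blood marks show that the EOS column was read correctly.

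**2. When do labs fall relative to the last dose?** Two years of 28-day cycles is 730/28 = 26.1, or about 26 cycles. The plan gives no cycle count, so I also tried 24 and 27. Last dose day = 1 + 28 × (cycles − 1), and the last chemistry and blood count fall 0 to 2 days before it:
- 24 cycles: dose on day 645, labs on days 643 to 645
- 26 cycles: dose on day 701, labs on days 699 to 701
- 27 cycles: dose on day 729, labs on days 727 to 729

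These days ignore the ±3-day visit window. In each case no chemistry, haematology or TSH is scheduled in the 100 days after the final dose. The same holds for any man who stops mid-cycle. A man stopped at a Day 1 visit may have labs that day, nominally 28 days after his last dose, and is not counted here.

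**3. Is the drug still present?** Section 1.5 gives a geometric mean half-life of 26.7 days. By simple first-order decay, the fraction left 28 days after a dose is 0.5^(28/26.7) = 0.48. The stated variability is wide (101%), so this is only a guide, but exposure clearly outlasts the scheduled labs.

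**4. Does another section fill the gap?**
- Section 14.3.2.1 promises blood tests but refers back to the calendar.
- Section 6.8 asks for a final evaluation on withdrawal from the protocol and names no labs.
- The 2-weekly assessments need a recognised toxicity, list no labs and may be remote.
- The day-100 contact is by phone or email.

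None schedules a test in a man without symptoms.

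**5. How many men?** The documents do not say. With an assumed share of the 34 stopping outside a Day 1 visit:
- 25%: 0.25 × 34 = 8.5, about 9
- 50%: 0.50 × 34 = 17
- 75%: 0.75 × 34 = 25.5, about 26

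For context, Section 1.9 puts grade 3-4 drug-related events at 18% or less: 0.18 × 34 = 6.1 men over the whole course. The part that is laboratory-only, silent and after the last dose is smaller and cannot be estimated from the documents.

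**The case against.** The best reply is that the gap is small in practice. PSA is drawn on Day 1, and scans are done up to 8 days before Day 1 or on it, so many decisions to stop should fall at a visit where labs are scheduled. For those men an EOS draw would largely repeat the Day 1 labs. This is a fair inference and argues for the lower end of the range. It does not help the 2-year completer, and it depends on results arriving before that day's dose, which the plan does not state.

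A second reply is that other protections exist. Section 14.3.2.1 requires a local physician, Section 11.2.3 follows AEs to resolution or stability, and men with toxicity are seen every 2 weeks. The renal, hepatic and endocrine algorithms in Appendix 1 are not visible to us. These narrow the gap for men with a recognised problem, but they act only once something has been noticed.

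Third, Day 1 labs reflect cumulative exposure, and a completer has been tested at every cycle, so only the tail is unseen. That stands. So does the limited effect on analysis. Section 12.2.2 summarises toxicity by maximum grade over time, and under Section 11.1.1 abnormal results "constitute AEs only if they induce clinical signs or symptoms or require treatment or further diagnostic tests". The AE summary is therefore less affected than the laboratory summary.

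Last, footnote g says only that research blood is generally drawn with the monitoring labs, and its later sentences concern treatment days. The ambiguity is a side point, and the finding does not depend on it.

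**Conclusion.** The concern holds. For 2-year completers and men who stop between a dose and the next Day 1, the plan schedules no chemistry, haematology or TSH after the last dose, and no other section supplies them. This follows directly from the calendar and the dosing day.

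The consequence is modest. It is a missed chance to detect silent laboratory toxicity, plus missing post-dose values in a descriptive laboratory summary. The primary endpoint and the decision rules are not involved. The count of about 9 to 26 men rests wholly on the assumed 25% to 75% share, and the number of events that would be missed cannot be derived. The change should be made because it is cheap and the gap falls on men who complete treatment as planned.

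**What to change.** Mark Chemistries, Hematology and TSH in the End of Study column, drawn with the PSA and research blood already due there. Add to footnote d that Day 1 labs drawn after the last dose, at the visit where treatment is stopped, may serve as the EOS labs, and that EOS values enter the laboratory-abnormality summary.

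**Cost.** At three assays per man, the maximum is 34 × 3 = 102. If Day 1 labs can stand in, the 25%, 50% and 75% scenarios give 8.5 × 3 = 25.5, 17 × 3 = 51 and 25.5 × 3 = 76.5 assays, or about 26 to 77. The visit is already in person and blood is already drawn, so the change is one calendar edit in an amendment, with no new visit.

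**Limit.** EOS falls within 30 days of the last dose, so at least 100 − 30 = 70 of the 100 AE-collection days would still rely on clinical contact. A further draw near day 100 would cover more, but that contact is now by phone or email, so it would need an extra blood-draw visit. It is optional and not part of this recommendation.
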